3.2 Secondary objectives

This principal research question will be broken down to the following sub aims:

1. Are there any established biochemistry, haematology and immunology blood tests that produce significantly different results in those who develop irAE when compared to those that don't. Including IL-6 (requires in-house verification). Observational study
2. Can a malondialdehyde LC-MS/MS assay suitable for clinical laboratory use be developed based on a method development by Sobsey *et al.*
3. Is malondialdehyde significantly raised in those who develop irAEs compared to those that do not. An ELISA kit has been located in the event an LC-MS/MS method is not successfully developed.
4. Can a blood test clinical algorithm be developed to stratify patients at high-risk of developing an irAE.

3.3 Outcome

This project could produce a clinical algorithm and/or blood test panel that successfully highlights patients at a high risk of developing irAE, prior to commencing therapy. This would allow closer monitoring of high-risk patients, leading to earlier diagnosis of irAE. Currently irAE can be tricky to diagnose and have overlapping symptoms with the malignancy and related concomitant treatments (27). Earlier diagnosis would lead to reduced hospitalisation, better outcomes, and reduced

BIO-CHECKPOINT

interruptions to the anti-cancer therapy, which may lead to better malignancy curative rates. There is also a potential to reduce morbidity and mortality risk for this subset of patients, as well as an overall reduction in resource burden.

4.0 STUDY DESIGN

4.1 SUMMARY OF DESIGN

This is a retrospective cohort study that looks at blood test results correlated to clinical outcomes.

Oncology patients, whom have been prescribed ICPIs for the first time, will be identified via the chemotherapy scheduling system. This study does not require extra blood draws or tubes to be taken. Left over serum and plasma from routine clinical blood draws will be retrieved. This serum and plasma will be aliquoted into tube labelled with a pseudonym reference. The samples will be booked into our laboratory information management system under a pseudonym reference. This system is password protected and only those involved in this research should be accessing these records. Left-over samples will be frozen at -80C and stored for a period of 1 month before being tested in batches. Before testing a list of NHS numbers of the patients that have been recruited will be sent to the Trust's data office. All samples for patients that have opted out of having their records used for research purposes will be destroyed in line with local pathology policy. Once testing is completed the left-over samples will be disposed of as in line with the Human Tissue Act, 2004 and local Portsmouth Pathology protocols.

[name] lead researcher will correlate the results to the patients' identifiers in a password protected sheet. Results will then be clinically correlated to patient's records to deem patient outcomes and if they had an irAE. Data will be correlated into a password protected excel sheet kept on Trust computer system. Data will then be de-identified and patient identification will be removed. Identifiable patient data will be removed for data analysis the spread sheet would contain age in years, sex, cancer type, ICPI type, if they had an irAE, irAE type and when it occurred. This data will be in a password protected excel sheet. Statistics will be carried out via R.

Minimal patient data will be used in the write up of this study i.e., age in years, sex, cancer type, ICPI treatment type, and if they had an irAE. Information about irAE will include type of event, and when it occurred post treatment.

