1.0 LAY SUMMARY –

Immune checkpoint inhibitors (ICPI) are a type of cancer treatment. Unlike traditional chemotherapy and radiation, which damages both the cancer and the healthy tissue, ICPI targets cancer directly by altering the immune system. Cancer cells produce high levels of protein called checkpoint proteins, which bind to white blood cells (which are part of the immune system) and stops them from working. Effectively the cancer is pushing a stop button on the immune system and the body can no longer fight it off. ICPIs block and remove these cancer checkpoint proteins, which allows the immune system to target the cancer again removing this stop button.

ICPI has great success in treating cancer and 10% of oncology NHS patients receive this treatment, although this number is increasing. However, ICPI carries a risk of a type of side effect called immune related adverse events (irAE). irAEs can be life threatening and present with similar symptoms to the patient's cancer. For example, a patient may have kidney cancer and after treatment with ICPI develop kidney failure. It is difficult for the doctor to tell if this is the cancer progressing or a side effect of the treatment. Delays in diagnosing irAE can lead to unnecessary hospitalisation, unnecessary breaks in treatment, lifelong side-effects, and death.

Currently there is not a unified blood test panel for ICPI patients, and the cancer societies have produced little guidance for the doctors to use. At Portsmouth what blood tests you get as an ICPI patient depend on which clinician you see. There is also little research as researchers are focussing on using blood tests to predict ICPI treatment success rather than the chance of a patient developing an irAE.

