2.0 BACKGROUND

This study aims to identify biomarkers that stratify Oncology patients on immune check point inhibitor (ICPI) that have an increased risk of developing autoimmune toxicity known as immune-related adverse events (irAE).

ICPIs are being increasingly prescribed and 10% of NHS Oncology patients receive treatment from this drug group (1,2). The reported rate of total irAE triggered by ICPI varies but is thought to be between 40-66% (3-5), a third of which are endocrine related (6,7).

Several bodies including the European Society for Medical Oncology, American Society for Clinical Oncology and the National Comprehensive Cancer Network have produced guidance for irAE management, but no unified screening protocol exists to stratify patients at high-risk (8). Currently the literature primarily centres around looking for prognostic biomarkers for treatment success rather than characterising toxicity.

Individual studies review the utilisation of some routine clinical blood tests, i.e., albumin, rheumatoid factor, lactate dehydrogenase, IL-6, etc, to screen and stratify high-risk patients (9,10). However, these tests are used in isolation and no singular clinical algorithm using a variety of routine tests has been developed for initial screening during ICPI therapy. A variety of protocols have been developed for screening endocrine irAE, although these are not consistently adopted, and practice varies.

ICPIs induce an enhanced immunological response to promote anti-tumour activity (11). There are a few forms of ICPI including CTLA-4 antibodies that upregulate T-cell activation pathways to enhance the tumour immune response. There are also antibodies that act as programmed death receptor agonists, which promote cytokine release and T-cell activation. (12)

An array of studies has shown that reactive oxygen species (ROS) are involved in the regulation of T-cell anti-tumour immunity (13–20). ICPI are active therapies that alter T-cell intracellular signalling, which can increase ROS production and proinflammatory cytokine secretion, thus exerting an immunotherapeutic effect (13).

irAE refers to a spectrum of autoimmune toxicities triggered by ICPI. ROS are implicated in the initiation, amplification, pathogenesis of autoimmune diseases (21,22). Are ROS heavily upregulated in irAE due to a dysregulated immune response and could the measurement of an oxidative stress marker act as a marker of toxicity?

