Malondialdehyde is generated from ROS driven lipid peroxidation of polyunsaturated fatty acids and is an indirect marker of oxidative stress. Malondialdehyde can be detected within plasma, serum and urine via liquid-chromatography mass-spectrometry (LC-MS/MS). (23–25) Malondialdehyde has been suggested as a future marker of tissue level thyroid dysfunction, the most common irAE is hypothyroidism (26).

BIO-CHECKPOINT

At present, Portsmouth does not have a unified screening process for patients about to commence ICPI and tests requested are clinician dependent. This project seeks to produce a unified clinical algorithm.

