3.0 Objectives and Outcomes Measures/Endpoints

3.1 Primary objectives

Can a clinical algorithm be created to flag high risk Oncology patients that have a greater risk of developing irAE? In addition, can novel biomarkers such as malondialdehyde be incorporated into this algorithm to aid stratification.

- P Oncology adult patients on ICPI
- I No intervention – retrospective analysis
- C Comparing blood test results of those who develop irAE to those who don't
- O Are any of the blood tests significantly different in those who develop irAE
- T 6 months follow up post starting treatment, 18 testing period.

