7.0 SAMPLE SIZE

All adult oncology patients at Queen Alexandra Hospital who are prescribed FDA approved ICPI for the first time, providing they don't meet the exclusion criteria will be recruited. The sample size is expected to be around 120 patients, based on ICPI patient Portsmouth Hospital University Trust data from 2022. It is estimated that around 40-66% of patients on ICPI will have an irAE based on the literature.

Assuming an incidence rate of 40% for irAE, this study would require at least a sample size of 47 individuals assuming a significance criterion of $\alpha=0.05$ and power =80.

The study will run for 18 months and hopes to obtain at least a sample size of 47 individuals, depending on how many patients are referred for ICPI therapy. The study will end before 18 months if we recruit 150 patients before the end date.

The period of testing was decided upon discussion with the Oncology department, based on ICPI prescriptions provided by the pharmacy department.

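### irAE status is read from routine records although testing depends on the clinician, so irAEs that only a blood test would show can fall by default into the comparator group

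*Combined protocol and SAP*

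**What the plan says.** **Outcome.** Section 4.1 (Summary of design) decides irAE status after the laboratory work, from care records: "Results will then be clinically correlated to patient's records to deem patient outcomes and if they had an irAE". Section 3.1 makes the contrast binary: "Comparing blood test results of those who develop irAE to those who don't". The sub-aims in section 3.2 use the same two groups, including the one on malondialdehyde. Follow-up is 6 months from the start of treatment.

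**Testing in routine care.** The lay summary (section 1.0) states: "At Portsmouth what blood tests you get as an ICPI patient depend on which clinician you see". Section 2.0 says of the period before treatment that "Portsmouth does not have a unified screening process for patients about to commence ICPI and tests requested are clinician dependent", and adds that endocrine screening protocols exist but are taken up unevenly.

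**Type of event.** Of all irAEs, section 2.0 says "a third of which are endocrine related", and that "the most common irAE is hypothyroidism".

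**What the study adds.** No sampling: "This study does not require extra blood draws or tubes to be taken". Under section 5.4, clinicians cannot see the study results, so a study test cannot lead to a recorded diagnosis. Nothing in the protocol uses study results to define the outcome, defines irAE, sets a minimum of follow-up testing, or says how a patient without the relevant test is to be classified.

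**The concern.** The study exists because testing of ICPI patients is inconsistent, yet its outcome depends on that testing. If a patient develops a thyroid or other endocrine irAE that only a blood test would reveal, and the clinician does not order the test within 6 months, the record shows no irAE. With two groups and no third category, that patient would by default be a comparator.

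Two things are at stake. First, true cases among the comparators shrink the difference for any marker that really predicts irAE. Second, if testing intensity varies by clinician or tumour group, a marker that differs between those groups can look predictive when it is not. The algorithm would then partly predict who gets tested. Symptoms are an imperfect safeguard, because section 3.3 says irAE symptoms overlap with those of the malignancy and its other treatments.

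**Working it through.** The protocol gives no figure for missed or unrecorded irAEs, so there is nothing of its own to reproduce on this point. The steps below use its figures where they exist and mark the rest as assumptions.

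**Inputs from the protocol**
- N = 120 expected patients (section 7.0).
- Incidence p = 40% to 66% (section 7.0): "It is estimated that around 40-66% of patients on ICPI will have an irAE based on the literature".
- Endocrine share of irAEs = 1/3 (section 2.0).

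**Assumptions**
- 20-50% of patients have no relevant on-treatment endocrine test, and 50-100% of endocrine irAEs among them stay unrecorded. The unrecorded share u therefore runs from 0.2 × 0.5 = 10% to 0.5 × 1.0 = 50%.
- None of these patients has another recorded irAE.
- A third of irAEs is read as a third of irAE patients.

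**Step 1: exposed cases.** irAE patients: 120 × 0.40 = 48 and 120 × 0.66 = 79.2. Endocrine: 48/3 = 16 and 79.2/3 = 26.4. True non-cases: 120 − 48 = 72 and 120 − 79.2 = 40.8.

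**Step 2: true cases in the no-irAE group.** Missed = endocrine cases × u. Contamination = missed / (true non-cases + missed).

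| Incidence | u | Missed | Contamination |
|---|---|---|---|
| 40% | 10% | 1.6 | 1.6/73.6 = 2.2% |
| 40% | 50% | 8 | 8/80 = 10.0% |
| 66% | 10% | 2.64 | 2.64/43.44 = 6.1% |
| 66% | 50% | 13.2 | 13.2/54 = 24.4% |

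**Step 3: relax the assumption of no other irAE.** If 25-50% of the missed patients also had another recorded irAE (assumption), they stay correctly classified. The upper figures fall to 6/78 = 7.7% and 4/76 = 5.3% at 40% incidence, and to 9.9/50.7 = 19.5% and 6.6/47.4 = 13.9% at 66%.

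**Step 4: dilution.** If missed and recorded cases have the same marker mean (assumption), the observed standardised difference is d × (1 − contamination). Section 7.0 states no effect size, so d = 0.526 is assumed; it gives 80% power for 48 versus 72 patients (two-sided t-test, α = 0.05). The assumption of no other recorded irAE applies again.

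| Incidence | Power, none missed | u = 10% | u = 50% |
|---|---|---|---|
| 40% | 80.0% | 77.8% | 68.0% |
| 66% | 77.3% | 73.3% | 57.5% |

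**Step 5: false association.** Suppose the true incidence is 40% in both halves of the cohort, with full detection in one half and 50% detection of endocrine irAEs in the other (assumption). The recorded rates are 40% and 40% − 0.5 × 13.3% = 33.3%. The odds ratio is (0.400/0.600)/(0.333/0.667) = 1.33, where the true value is 1.

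**The case against.** The strongest reply is that this is an inference. A reader might take the protocol to rule that untested patients count as having no irAE. It does not: it says only that records are used to decide the outcome. What it shows is a binary comparison with no definition of irAE and no provision for patients not assessed. That is enough for the default described here, but it is not a stated rule.

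Three other strong readings also fail.
- A reader might infer from the list of spreadsheet items in section 4.1 that tested-and-normal could never be told apart from never-tested. The list is not exhaustive, since it also omits every blood result, and the laboratory system is already reviewed daily (section 5.1). The data can be retrieved; the plan does not say that they will be.
- A reader might take thyroid disease to be the stated reason for measuring malondialdehyde. Section 2.0 gives a general oxidative-stress rationale, with thyroid dysfunction in one sentence. No endocrine-specific comparison is planned.
- The section 2.0 sentence on local screening concerns patients about to start treatment. Only the lay-summary sentence covers local ICPI patients in general, and it does not say that thyroid tests are omitted or how often.

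On size, the objection largely stands. The detection rates are assumed. The upper end needs half the patients untested and every endocrine irAE among them unrecorded, symptomatic ones included. The 40-66% is itself a reported rate, so subtracting missed cases from it may double count. At the low end with 40% incidence the power loss is about 2 points. Finally, using routine records is a deliberate choice to limit the burden on staff (section 4.5). That explains the choice but does not remove the dependence of the outcome on testing.

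**Conclusion.** The point holds in a conditional form. Followed as written, the plan can place patients with unrecorded, laboratory-detected irAEs in the comparator group, and it ties the outcome to how intensively each patient was tested. Nothing in the study design fills that gap.

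The size is unknown. Contamination of 2-10% at 40% incidence, or 6-24% at 66%, rests on the assumed 10-50% of endocrine irAEs unrecorded and on no missed patient having another recorded irAE. These figures lean high. At the lower end the effect on power is minor; at the upper end the loss is about 12 points at 40% incidence and 20 at 66%, for the assumed effect. A false association additionally requires testing to vary with something related to the marker, which the protocol makes plausible but does not show. The practical case for acting is that, unless testing is recorded, neither the investigators nor a reader can tell which end of the range applies.

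**What to change.** 1. Add to the section 4.1 extraction, from the laboratory system, whether and when each patient had on-treatment thyroid tests and other tests relevant to irAEs, from first dose to 6 months. Specify these fields before results are linked to records.
2. Keep the planned any-irAE comparison, including that for malondialdehyde, as the main analysis.
3. Beside it, report a sensitivity analysis restricted to patients with at least one on-treatment thyroid test. Apply the restriction to patients with and without irAE alike; removing only untested irAE-negative patients would inflate the apparent incidence.
4. Tabulate testing by tumour group and ICPI type.
5. If any endocrine-specific comparison is made, treat untested patients as not assessable.

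An analysis that counts only symptomatic irAEs is not advised unless detected asymptomatic cases are excluded from it; otherwise known cases would move into the comparator group.

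**Cost.** A few extra columns from a system already in use, one sensitivity analysis and one table. No extra blood and no change to care. The tested-only analysis is smaller and itself selective, because symptoms can prompt testing, so it supplements the planned analysis and does not replace it.

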5.4 REPORTING OF ACTIONABLE RESULTS

Critically abnormal results may be produced during this study. To avoid moral dilemma of if to report results that the clinician did not request the following mitigating factors have been put into place. Samples will be labelled and booked in under a pseudonym and only the lead researcher will have access to the key and relevant patient identifiers. Samples will be batched and run once a post collection, making these results historic values. Results will not be clinically correlated to patient outcomes until May 2025 meaning outcomes of any abnormal results would have likely presented by this point. Clinicians will not see or be able to look up the study's results.

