6. DATA PROCESSING

6.1 DATA TRANSFER AND STORAGE

Results will be anonymised under a pseudonym/reference on the laboratory information management system (APEX). This is a password protected system that only authorised personnel can access on password protected Trust accounts, which are also password protected. The patients' clinicians will not be able to see these results or link them to their patients. Only those on the research team will be able to de-anonymise the data. Results will be stored on APEX during the study. Post study completion the results will be extracted from APEX into a password protected excel sheet. Results and patient identifying data will not be sent outside of the Trust.

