9.0 HEALTH RELATED FINDINGS

Samples will be stored and tested under a pseudonym/reference one month post initial collection. Clinicians will not have access to these results and those testing the samples will not know who the sample belongs to. Results will not be linked to the patients' records until completion of the data collection period i.e., May 2025.

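### Study results are joined to identified patients before irAE status is decided, and nothing in the plan keeps whoever decides it from seeing malondialdehyde and the other study-only results

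*Combined protocol and SAP*

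**What the plan says.** Section 4.1 gives a sequence. First, the "lead researcher will correlate the results to the patients' identifiers in a password protected sheet". Next, "Results will then be clinically correlated to" the patient's records "to deem patient outcomes and if they had an irAE". De-identification for analysis comes only after that.

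The sentence about deciding irAE status does not say who decides. Section 5.4 says that "only the lead researcher will have access to the key and relevant patient identifiers", and section 6.3 gives linkage to one person. The section on the role of sponsor and funder makes the lead researcher responsible for analysis and interpretation as well.

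Two groups are masked. Section 9.0 states: "Clinicians will not have access to these results and those testing the samples will not know who the sample belongs to". Sections 5.4 and 9.0 also put off linkage until May 2025. Section 6.1 adds: "Post study completion the results will be extracted from APEX into a password protected excel sheet".

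On the outcome, section 3.3 says: "Currently irAE can be tricky to diagnose and have overlapping symptoms with the malignancy and related concomitant treatments". On the hypothesis, the third aim in section 3.2 has a direction: "Is malondialdehyde significantly raised in those who develop irAEs compared to those that do not".

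**The concern.** irAE status is the grouping variable for every biomarker comparison and for the algorithm. If an unclear case is labelled with the study results in view, the label can lean towards the hypothesis. The marker is then tested against an outcome that it helped to define. That raises the false-positive rate and the apparent accuracy of that marker and, to a lesser degree, of markers correlated with it. Unrelated markers are not affected.

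Malondialdehyde is the most exposed. It is the novel marker, it is not part of routine care, and its aim states the expected direction. Section 13.0 intends a test panel for all ICPI patients on the strength of these results. Once labels have been assigned with results in view, the bias can be neither measured nor cleanly undone.

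**Working it through.** **1. Order and masking, from the text**

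| Step or safeguard | Section | Does it mask whoever decides irAE status? |
|---|---|---|
| Results joined to identifiers | 4.1 | No; this comes first |
| irAE status decided from records | 4.1 | This is the decision at issue |
| De-identification | 4.1 | No; it comes afterwards and protects confidentiality |
| Treating clinicians cannot see results | 5.4, 6.1, 9.0 | No, but it keeps recorded diagnoses blind |
| Sample testers do not know the patient | 9.0 | No |
| Linkage held until May 2025 | 5.4, 9.0 | No; it is a delay |

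The text contains no irAE definition, no adjudication rule and no outcome lock before linkage.

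**2. Possible size**

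The plan has no figure of its own to reproduce. From section 7.0 come the 40% irAE rate, alpha 0.05, about 120 expected patients and the minimum of 47. Assumed: a marker with no true association; a fraction *a* of patients whose status is unclear; and an assessor who calls an unclear case irAE with probability *p* if the marker is above its median and 1−*p* if below. The test is a two-sided t-test.

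Simulated false-positive rate at N = 120 (20,000 studies per cell):

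| Unclear cases | Sway 55/45 | 65/35 | 80/20 |
|---|---|---|---|
| 5% | not run | 4.8% | not run |
| 10% | 5.3% | 5.9% | 8.4% |
| 20% | 5.3% | 8.6% | 19.2% |
| 30% | 5.9% | 12.6% | 36.0% |

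A hand check for *a* = 0.20, *p* = 0.65, N = 120, with the marker in SD units:

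- Labelled irAE rate: q = (1−a)×0.40 + a×0.50 = 0.32 + 0.10 = 0.42.
- Spurious mean difference: a(2p−1)×0.399 / [q(1−q)] = 0.20×0.30×0.399 / 0.2436 = 0.098 SD. Here 0.399 is half the mean absolute value of a standard normal.
- Standard error: 1/√[N q(1−q)] = 1/√(120×0.2436) = 0.185.
- Shift of the test statistic: 0.098/0.185 = 0.53.
- Rejection probability: P(Z > 1.96−0.53) + P(Z < −1.96−0.53) = 0.076 + 0.006, or about 8.3%.

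The same formula gives 18.6% for 20% unclear at 80/20 and about 36% for 30% at 80/20, in line with the table.

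At N = 47 the rates are lower: 5.1% and 6.3% (10% unclear, 65/35 and 80/20), 6.3% and 10.4% (20%), 7.5% and 16.7% (30%; the formula gives 7.9% and 16.9%). A larger sample makes the problem worse, because the spurious difference is fixed while the standard error shrinks.

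Further simulation results at N = 120:

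| Quantity | 20%, 65/35 | 20%, 80/20 | 30%, 80/20 |
|---|---|---|---|
| Mean apparent AUC of the useless marker | 0.53 | 0.56 | 0.59 |
| False positives, second null marker correlated 0.5 with the first | 5.9% | 8.5% | 12.1% |
| False positives with unclear cases left out | 5.0% | 5.2% | 4.7% |

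A second null marker uncorrelated with the first stays at 4.8% to 5.4%.

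A different model was also run: the unclear-case irAE probability is 0.4 plus or minus a lean of 0.2 to 0.4, with a Mann-Whitney test. At N = 120 it gives 6.4% to 11.6% with 10% unclear and 12.2% to 32.6% with 20%. The direction is the same and the assumed sway is stronger. With no unclear cases it gives 4.4% to 5.0% across both sample sizes.

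**The case against.** The best defence is that most irAE labels will be copied from diagnoses made by clinicians who could not see the study results. The wait until May 2025 gives those diagnoses time to settle in the notes, so few cases may need judgement. This stands as a limit on the size of the problem. It does not close the gap, because the protocol nowhere confines abstraction to recorded diagnoses. Section 9.0 could be read as having outcomes collected before linkage, if its data collection period includes outcome data; section 4.1 states the opposite order.

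That the lead researcher makes the call is an inference. If someone else does, section 4.1 still has that person working from linked results. Section 4.4 refers to a flow chart and working instructions whose content was not available for this review, so the conclusion rests on the protocol text.

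The magnitudes depend wholly on assumptions. One marker driving every unclear call is a strong model, since the sheet will hold many results and malondialdehyde has no routine local cut-off. If the sway on any one marker were a quarter as large, the rates at N = 120 would fall to 5.1% (20%, 65/35), 5.8% (20%, 80/20) and 7.0% (30%, 80/20). The 36% figure is an extreme, not an expectation.

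Two objections to the remedy also stand in part. Results sit on APEX during the study, so the key-holder could still look. And leaving out unclear cases restores 5% in the simulation because they were drawn at random; real unclear cases may differ from the rest, so that analysis can bring its own selection and loses patients.

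**Conclusion.** The concern holds. As written, section 4.1 puts linkage before the irAE decision, and no safeguard in the protocol applies to the person making that decision. The effect on malondialdehyde and other study-only tests runs from essentially none (about 5%) to 8.6% and 19.2% with 20% of cases unclear at 65/35 and 80/20, and 36.0% at the far end, for 120 patients. These figures rest on assumed ambiguity and sway, for which the documents give no values, and on the abstractor having to judge some cases. Confidence in the size is therefore no more than medium. The order and the lack of masking do not depend on those assumptions. This should be changed before outcomes are abstracted.

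**What to change.** In section 4.1, set the order as follows:

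- After each patient's 6-month follow-up, abstract irAE yes/no, type and onset date from the clinical records against a written irAE definition.
- Mark each status as a clinician-recorded diagnosis or an abstractor judgement.
- Date and lock the outcome sheet before any study result is extracted from APEX, then merge the results by pseudonym.

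In section 6.1, add that the post-study extraction happens only after this lock. Add one sensitivity analysis that leaves out the abstractor-judged cases, reported beside the main analysis and not in place of it.

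The cost is a short definition, one extra column and a dated lock. Extraction is already planned for after study completion, so the timetable need not change, and no additional assessor, sample or patient is required. Two limits should be stated: routine results in the clinical record remain visible, and the lock relies on the key-holder not looking at APEX earlier. The protection is therefore mainly for malondialdehyde and the other study-only tests.

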4.2 ELIGIBILITY CRITERIA

Inclusion criteria

- ≥ 18 years of age
- All sex
- Oncology patients
- Who is prescribed FDA approved check point inhibitors: (ipilimumab, nivolumab, pembrolizumab, cemiplimab, atezolizumab, avelumab, and durvalumab)

BIO-CHECKPOINT

- All cancer subtypes are included

Exclusion criteria

- <18 years of age
- Those previously been treated with checkpoint inhibitors.
- Those with a previous medical history of autoimmune disease
- Those with previous medical history of endocrine diseases
- Those with a pre-existing malignancy
- Non-Queen Alexandra hospital oncology patients
- Lacking capacity to consent

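### No field for other anticancer treatment or immunosuppression is planned, so the comparison of blood tests by irAE status cannot be adjusted for, or described by, co-treatment

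*Combined protocol and SAP*

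**What the plan says.** Section 4.1 describes the de-identified sheet used for analysis: "the spread sheet would contain age in years, sex, cancer type, ICPI type, if they had an irAE, irAE type and when it occurred". The list for publication has the same scope: "Minimal patient data will be used in the write up of this study i.e., age in years, sex, cancer type, ICPI treatment type", followed by irAE status, type and timing. Neither list has a field for chemotherapy, radiotherapy, other systemic anticancer drugs, corticosteroids or other immunosuppressants, and no other section adds one.

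Section 4.2 states "All cancer subtypes are included" and admits seven checkpoint inhibitors. The only treatment it excludes is a previous checkpoint inhibitor.

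Section 3.3 acknowledges the diagnostic difficulty: "Currently irAE can be tricky to diagnose and have overlapping symptoms with the malignancy and related concomitant treatments". The outcome comes from routine records: "Results will then be clinically correlated to patient's records to deem patient outcomes and if they had an irAE". No definition of an irAE and no rule for attributing an event are given.

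Section 3.1 sets the comparison as "Comparing blood test results of those who develop irAE to those who don't". No covariates are named. The only other statement on analysis is that R will be used.

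**The concern.** The study pools patients with different regimens and treatment histories, and co-treatment can enter the comparison by two routes.

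- **Confounding.** Treatment given before the draw, or ongoing at it, may shift a blood test. If the same treatment is also linked to being recorded as an irAE, a marker unrelated to irAE will differ between the two groups.
- **Mislabelling.** Toxicity from any co-treatment, including treatment begun together with the ICPI, may be recorded as an irAE. This route does not need the marker to move.

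The purpose is a panel or algorithm for all ICPI patients (sections 3.3 and 13.0). Under the first route, that algorithm could partly flag who had received other treatment, which the oncology team already knows. The malignancy half of the overlap named in section 3.3 has a field (cancer type). The treatment half has none. A variable that is not collected cannot be adjusted for, stratified on or tabulated.

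**Working it through.** **The plan's own figures.** The plan gives no figure on this point. Section 7.0 supplies N (about 120 expected, 47 minimum) and an irAE incidence of 40%, within a cited range of 40-66%. It gives no effect size, so the 47 cannot be derived from its stated inputs. It is used here only as a sample size.

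**Assumed inputs, none of them in the documents.**
- Share co-treated at or before the draw: c = 0.2 to 0.5.
- Marker shift from co-treatment: d = 0.5 to 0.8 SD.
- Recorded irAE rate without and with co-treatment, p0 and p1: 35% v 50%, or 30% v 55%.
- Given co-treatment, the marker has no relation to irAE.
- Unadjusted two-sample t-test, two-sided 5%. The plan states neither the test nor its sidedness.

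**Formulas.**
- Overall irAE rate: q = c·p1 + (1−c)·p0.
- Share co-treated among irAE patients: a = c·p1/q. Among the others: b = c(1−p1)/(1−q).
- Spurious difference: D = d(a−b).
- Within-group variance: V = 1 + d²[q·a(1−a) + (1−q)·b(1−b)].
- Standard error: √(V/[N·q(1−q)]), and λ = D/SE.
- False-positive rate ≈ Φ(λ−1.96) + Φ(−λ−1.96).

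**Worked case** (N=120, c=0.5, d=0.8, 30% v 55%).
- q = 0.275 + 0.15 = 0.425.
- a = 0.275/0.425 = 0.647; b = 0.225/0.575 = 0.391.
- D = 0.8 × 0.256 = 0.205 SD.
- V = 1 + 0.64 × (0.097 + 0.137) = 1.150.
- SE = √(1.150/29.325) = 0.198, so λ = 1.03 and the rate is 17.8%.
- Simulation gives 16.8% (8,000 runs) and 17.6% (40,000 runs).

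**All corners at N=120** (formula; simulation in brackets).

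| Co-treated | Shift | 35% v 50% | 30% v 55% |
|---|---|---|---|
| 20% | 0.5 SD | 5.8% (6.0%) | 7.4% (7.3%) |
| 20% | 0.8 SD | 7.0% (6.8%) | 10.8% (10.8%) |
| 50% | 0.5 SD | 6.9% (6.5%) | 10.3% (10.4%) |
| 50% | 0.8 SD | 9.5% (9.0%) | 17.8% (16.8%) |

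At N=47 the formula gives 5.3-9.9% over the same corners, and simulation about 5.5-9.5%.

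**Both links are needed.** With d=0, or with equal irAE rates, D=0 and the rate is 5%. In separate simulations of 20,000 runs (30-50% co-treated, shifts up to 1 SD), putting co-treatment in the model kept the rate at about 5% (4.7-5.5%).

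**Mislabelling route.** Suppose the whole excess c(p1−p0) were co-treatment toxicity recorded as irAE. Its share of recorded irAEs is then c(p1−p0)/q.
- Lowest: 0.2 × 0.15/0.38 = 8%.
- Highest: 0.5 × 0.25/0.425 = 29%.

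If the marker is unaffected and these patients resemble those without irAE, a real marker difference shrinks by the same percentage. The false-positive rate stays at 5%.

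**The case against.** Several stronger readings are tempting. The documents do not support them.

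- **That section 3.3 says chemotherapy, radiotherapy or steroids mimic irAEs.** It refers to related concomitant treatments and names no class. Corticosteroids are mentioned nowhere.
- **That the plan concedes these treatments move the blood tests.** It does not. The lay summary says only that chemotherapy and radiation damage healthy tissue. The marker shift is an assumption.
- **That all co-treatment acts on both marker and outcome.** Section 3.3 aims to flag patients before therapy, and section 5.1 lists patients who have yet to start the ICPI. The draw time is not fixed explicitly, but this points to a pre-ICPI sample, which treatment begun with the ICPI could not shift. For that treatment only mislabelling remains.
- **That the gap can never be repaired.** Sections 6.1 and 6.3 keep a linkage through the pseudonym, and data are held for a year after completion. Co-treatment is unplanned, not irrecoverable. Relinking after results are seen is still weaker than planned capture.
- **That the field list is exhaustive.** It sits in a passage on de-identification and also omits the blood results. Even so, no other section adds co-treatment.

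Two further objections stand in part. Cancer type and ICPI type may partly stand in for regimen, but they do not show whether another agent was given or what was ongoing at the draw. And a co-treatment column does not correct a wrong irAE label. That also needs an attribution rule, which is a separate gap.

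**Conclusion.** The omission is real and worth correcting before linkage. As written, the plan can neither adjust for nor describe co-treatment, although it names concomitant treatment as a source of diagnostic overlap and admits patients without restricting it.

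The consequence is conditional. Over the assumed ranges, the per-marker false-positive rate is about 6-17% at N=120 (17-18% at the extreme corner) and about 5.5-9.5% at N=47. The high end needs half the patients co-treated, a 0.8 SD shift and a 25-point gap in recorded irAE rates, all together. A reader might infer that any marker found here will be a co-treatment marker. The documents do not support that, because they give neither the prevalence of co-treatment nor its effect on any test.

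**What to change.** Add to the section 4.1 field list, before de-identification:

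1. Other systemic anticancer treatment given with the ICPI.
2. Anticancer treatment, systemic corticosteroid or other immunosuppressant given before the draw or ongoing at it.

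Record the timing of each relative to the draw. The sources are the chemotherapy scheduling system, already checked daily on weekdays (section 5.1), and the patient records already opened to determine outcome.

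Pre-specify one adjusted or stratified version of the main comparison of irAE with no irAE, using a single co-treatment indicator. Add further terms only if the number of irAEs allows: 40% incidence gives about 19 events at N=47 (0.40 × 47 = 18.8) and 48 at N=120. Report irAE rates by co-treatment.

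Treat the subset without co-treatment as descriptive. With half the patients co-treated and a 30-35% irAE rate in the rest, it would hold only about 7-8 irAEs at N=47 (23.5 × 0.30 to 0.35) and 18-21 at N=120 (60 × 0.30 to 0.35).

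The cost is a few columns, one or two degrees of freedom and a minor amendment. No extra blood or patient contact is needed.
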